## TRIAL SUMMARY

Trial Title	A PROSPECTIVE, MULTI-CENTER, RANDOMIZED, PARALLEL-GROUP CONTROLLED TRIAL TO COMPARE CONSERVATIVE VERSUS SURGICAL TREATMENT IN PERONEAL NERVE ENTRAPMENT
Short title	FOOT DROP: Follow-up and Outcome of Operative Treatment with Decompressive Release Of the Peroneal nerve
Trial Design	
This is a prospective, multi-center, randomized, parallel-design study.
 
This is a superiority trial: the goal is to prove superiority of surgery to maximal conservative treatment.
 
Subjects will be randomized 1:1 to surgery or to conservative treatment. No cross-over is allowed until the primary endpoint is assessed at 9 months after randomization. After the primary endpoint is assessed, cross-over to surgery is allowed, with extended follow-up at 18 months after randomization (equals 9 months after primary endpoint).

Trial Participants and setting	Patients with electrodiagnostic (EDX)-documented peroneal nerve entrapment with persisting foot drop 10 +/- 4 weeks after onset of symptoms will be included in the trial. Imaging to exclude a compressive mass at the level of the fibular head is required, since these patients are excluded from the trial. Included patients will be allocated to either surgical decompression of the peroneal nerve or maximal conservative treatment.
Intervention	Decompressive release of the peroneal nerve at the level of the fibular head.
Control	
Maximal (prolonged) conservative treatment with physiotherapy aiming at muscle strengthening and gait rehabilitation.
 
Allowed: use of foot-ankle orthosis / electrostimulation and other therapies reflecting daily practice.

Primary Endpoint	Difference in distance (in meters) covered during the six-minute walk test between baseline and 9 months after randomization

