### **Subgroup analysis**

A literature search was performed to identify predictors of good and bad outcome after surgical or conservative treatment. There is only limited data available and the data discussed come from several retrospective patient series (3, 38, 39, 43, 44, 63), one prospective conservative multicenter trial (28), one prospective case series (40) and one meta-analysis (58). Based on the cited articles, the following predictors of outcome will be used for further analysis:

1. Diabetes
2. Smoking (No, history, current)
3. Rapid/significant weight loss (> 5% of total body weight (18, 64))
4. High age (> 60 years)
5. Prolonged squatting

These predictors will be used in an exploratory analysis for the primary and key secondary endpoint (see Section 11). In this way, interactions between the predictor and a possible treatment effect can be identified and several new hypotheses can be generated to be investigated in further trials (where several subgroups could be studied in further detail).

-

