Suppose the baseline mean 6MWD is 300 meters in the conservative arm and surgical arm of the trial (no difference due to randomization). Mean difference in 6MWD in the surgical arm between baseline and 9 months is 120 meters and mean difference in 6MWD in the conservative arm between baseline and 9 months is 100 meters. Therefore, the difference between both groups is 20 meters. Apart from the assessment of statistical significance, the clinically relevant difference will be defined as the minimum of 10% of the mean minimal predicted age- and sex specific reference value of all patients in the conservative and surgical arm. E.g. assuming an average age of 55 years and 42% of the patients being female(3), the minimal mean predicted 6MWD would be 551.86 meters, resulting in a MCID of 55.2 meters. The actual value applied will be determined by the trial population.

Standardized 6MWT methodology is essential for reproducible and reliable results. The test should be performed in a minimally trafficked area along a flat, straight corridor ideally ≥ 30 meters in length (90, 91). Although the procedural guidelines, formulated in 2002, were made to address patients with respiratory pathology, several items can make the 6MWT in the foot drop trial more standardized:

1. Mark the starting line with brightly colored tape.
2. Mark the length of the hallway every 3m.
3. Mark turn around with a cone.

4. Patients should be wearing comfortable clothing and use their usual walking aids. The use of a foot-ankle orthosis is prohibited.
5. The patient should rest for at least 10 min prior to commencement of testing.
6. Patients should not have exercised vigorously within 2 hours of beginning the test.
7. All patients will be instructed to cover as much distance as possible during six minutes.
8. Subjects will be encouraged every minute. The remaining time will be communicated every minute. An example: When the timer shows 3 minutes remaining, tell the patient the following: "You are doing well. You have only 3 minute left."
9. If the patient stops during testing, the timer should not be stopped. The time at which the patient stopped, and recommenced walking should be noted.
10. Walk distance is measured by counting the number of full laps and rounding to the nearest meter for the partial final lap.

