# 11 STATISTICS AND DATA ANALYSIS

## 11.1 Sample size calculation

Given that no reliable estimates of the 6MWD are available in this population, the sample size calculation is performed assuming a moderate effect size (mean difference divided by the standard deviation). Based on an effect size of 0.5, 172 patients would have 90% power to show a significant difference at a two-sided significant level of 5% in the change in the 6MWD from baseline to 9 months after randomization using a t-test. The sample size calculation was performed with G\*Power, version 3.1.9.4. To compensate for an expected 5% dropout, a total of 182 patients (91 patients per group) will be included. The expected dropout rate of 5% is based on the results of patients interviews and a large, multicenter, randomised controlled trial comparing surgery versus non-surgery (or delayed surgery) with a design very similar to the foot drop trial (61, 62).

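### The exploratory treatment-by-age interaction uses age cut at 60 although age is recorded in years; if the effect changes gradually with age, this discards roughly 40 to 50% of the information

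*Protocol*

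**What the plan says.** The Subgroup analysis part of Section 5.1 names five predictors of outcome, drawn from a literature search. Age enters as "High age (> 60 years", that is, as two groups. The section states the use: "These predictors will be used in an exploratory analysis for the primary and key secondary endpoint". It also states the aim, which is that "interactions between the predictor and a possible treatment effect can be identified", so that hypotheses can be passed on to later trials.

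Section 8.6 (Baseline data) records age in years, and Section 7.1 admits anyone aged 18 or over with no upper limit. The protocol names no other form of age for this analysis. Section 5.1 refers onward to Section 11. That section does not describe the subgroup model, and it leaves the full details of the primary and key secondary analyses to the SAP. Section 11.4.4 says that the study is powered only for the primary endpoint.

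**The concern.** Cutting a measured variable in two treats a patient of 61 like one of 85, and a patient of 59 as different from one of 61. For an interaction analysis this matters in two ways. A gradual change of the surgical effect with age becomes harder to see, and the answer depends on where the cut happens to lie.

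Nothing else in the protocol works with a step at 60 years: randomisation is simple and unstratified (Section 8.3), and no eligibility rule or analysis decision uses that age. Elsewhere the protocol treats age as a gradient for the same outcome. Its reference equation lowers the predicted six-minute walk distance by 2.99 m per year of age. That is a main effect and not an interaction, but it shows that age on its natural scale is already in use.

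What is at stake is the stated purpose of the analysis. An exploratory analysis that is insensitive to a gradient may fail to pass on the hypothesis it was meant to find.

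**Working it through.** **The plan's own figures first.** Section 11.1 says "Based on an effect size of 0.5, 172 patients would have 90% power", at a "two-sided significant level of 5"%. A two-sample t-test with effect size 0.5 needs 85.03 per arm, so 86 per arm and 172 in total (power 90.3%). Allowing for 5% dropout, 172 / 0.95 = 181.05, which rounds up to 182 with equal arms. Both figures reproduce. The evaluable number, 172, is the right base for what follows. The protocol states no power for any interaction.

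**Inputs for the age question**
- Cut: 60 years (Section 5.1).
- Mean age: 55 from the worked example in Section 8.7.5 ("assuming an average age of 55 years and 42% of the patients being female"). 50 is added as an assumed alternative.
- SD of age: not given. 12 and 15 years are assumed.
- Shape: age roughly normal, treatment effect linear in age (both assumed).

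**Formula.** Let c = (60 − mean) / SD and p = Φ(c), the share at or below 60. The information kept by the two-level form, relative to age in years, is the squared correlation between age and its indicator:

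RE = φ(c)² / [p(1 − p)]

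Worked case, mean 55 and SD 12: c = 5/12 = 0.417, φ(c) = 0.366, p = 0.662. So RE = 0.1338 / 0.2239 = 0.598.

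| Mean / SD | Share over 60 | Information kept | Loss | 172 patients work like |
|---|---|---|---|---|
| 55 / 12 | 34% | 59.8% | 40.2% | 103 |
| 55 / 15 | 37% | 61.1% | 38.9% | 105 |
| 50 / 12 | 20% | 49.2% | 50.8% | 85 |
| 50 / 15 | 25% | 54.1% | 45.9% | 93 |

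**Sensitivity to the assumed distribution.** At mean 55, widening the SD to the range 10 to 18 gives losses of 41.9% to 38.1%. For a normal distribution the smallest possible loss is 36.3%, reached when the cut is at the median. For uniform ages RE = 3p(1 − p). Over 20 to 80 this is 3 × 2/3 × 1/3 = 0.667 (loss 33%), and over 30 to 80 it is 3 × 0.6 × 0.4 = 0.72 (loss 28%).

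**What this means for power.** Take N = 172, 1:1 allocation, residual SD 1 and a normal approximation. The standard error of a linear interaction per SD of age is 2/√172 = 0.1525. With the cut, the detectable signal shrinks by √RE. For mean 55 and SD 12 to 15:
- Interaction of 0.3 SD of outcome per SD of age: 50% power with age in years, 33 to 34% with the cut.
- Interaction of 0.4: 75% against 53 to 54%.

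Power is low in any case. With 34% of patients over 60, the standard error of the two-group interaction is √[4/(172 × 0.338) + 4/(172 × 0.662)] = 0.322. A difference between the age groups as large as the whole planned treatment effect (0.5 SD) then has about 34% power.

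**If the truth is a step.** A simulation (N = 172, age normal with mean 55 and SD 15, clipped to 18 to 90, 4,000 runs per case) compared the two forms under each truth:
- Linear interaction of 0.4 SD per SD of age: 71% power with age in years, 50% with the cut.
- Step of 0.8 SD at 60: 51% with linear age, 71% with the cut.

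The advantage therefore depends on the shape of the interaction.

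**The case against.** Four things can be said for the plan.

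- **The analysis is exploratory.** No claim, significance level or decision depends on it, and superiority rests on the overall nine-month comparison (Section 11.4.3). This stands and fixes the point as minor. It does not remove it, because finding interactions is the stated aim.
- **Modelling detail belongs in the SAP.** The protocol gives no interaction model, and the SAP, which is not shown, may add age in years. That is fair, but the two-level form is written in the protocol itself, so it can be reviewed as stated.
- **The cut is pre-specified and said to rest on cited articles.** Pre-specification does remove the danger of choosing a cut from the data. Whether the cited articles support a threshold at 60 cannot be judged from the protocol, which gives no evidence of one.
- **If the effect steps at 60, the cut is the better analysis.** This stands. A reader might infer that the two-level comparison should be reduced to display only, at no cost. The documents do not support that, since they show neither a gradient nor a step.

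A reader might also extend the point to "Rapid/significant weight loss (> 5% of total body weight"). That does not follow. The predictor combines speed and size of loss, and Section 8.6 records rapid onset separately. Weight loss is only one of several risk factors, so many patients may have none, and the normal-theory loss does not carry over to such a distribution.

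**Conclusion.** The point holds as a minor improvement, limited to age. Under a roughly normal age distribution (mean 50 to 55, SD 12 to 15) and an interaction linear in age, the cut at 60 keeps about 49 to 61% of the information, so 172 evaluable patients work like about 85 to 105.

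A reader might take a loss of about 40% as a fixed property of this trial. It is not: that figure needs a mean near 55, approximate normality and linearity, and the protocol supplies only the mean, as an example. The loss is 28 to 33% for the uniform distributions tried, and nil for a true step at 60. The validity and power of the primary comparison are untouched.

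**What to change.** In the Subgroup analysis part of Section 5.1, make the treatment-by-age interaction with age in years (linear or spline) the main exploratory age analysis, and report the estimated treatment effect with its confidence interval at a few ages chosen in advance. Keep the pre-specified comparison of over 60 with 60 or under alongside it as a supporting analysis, so that a step would still be seen.

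The cost is a line or two of text and one more exploratory result. No new data are needed. If the effect really does step at 60, the main age analysis will have somewhat less power than the cut, which is why the two-group comparison should stay.

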## 6 STUDY SETTING

The foot drop trial is a multicenter study.. In function of the recruitment rate, up to 23 Belgian centers and 5 Dutch centers will participate in the trial.

In each participating centre, there should be a department of neurosurgery, neurology and physical medicine/rehabilitation. The departments of orthopaedic surgery and plastic and reconstructive surgery will be involved as well if they are routinely involved in this patient care. To accentuate the multidisciplinary collaboration throughout the study, a non-surgical adjunct principal investigator should be appointed in each centre. There needs to be at least one neurologist/rehabilitation physician that is thoroughly trained in electrodiagnostics and has experience with the interpretation of electrophysiological investigations in patients with peripheral nerve entrapment. Since all patients are diagnostic using electrodiagnostics, the adjunct principal investigator is preferably the local electrophysiologist.

The surgical procedure is not considered very complex. Therefore, every general neurosurgeon is qualified to perform the procedure in participating patients. A neurolysis can also be performed by an orthopaedic surgeon with experience in peripheral nerve surgery. Preferentially, every participating centre has an experienced peripheral nerve surgeon. The rehabilitation program can be organised within the participating center or in an ambulant setting, with physiotherapists working according to the proposed guidelines (designed to be a mirror of current daily practice).

The blinded researcher (or outcome assessor), can be a site-specific clinical trial assistant, study-nurse, physiotherapist, resident or other qualified medical professional. The blinded assessor is preferably an independent physiotherapist. At each participating site, the (blinded) researchers will be trained in certain clinical assessments including isometric dynamometry and MRC-scoring for ankle dorsiflexion, hallux extension and ankle eversion. Training videos will be made available, so that a uniform assessment can be made in the different centers and inter-observer variability can be reduced to the minimum. These training videos will be shown at the site initiation visit and will be accompanied by a questionnaire. In this way, it can be guaranteed that the training has been followed.

The majority of patients with peroneal nerve entrapment and foot drop present in an emergency setting. Most often, these patients are referred by general practitioners because of sudden gait difficulties and an increased risk of falling. Sometimes the reason for referral is further diagnostics since foot drop has a broad differential diagnosis, and some diagnoses require (semi-)urgent treatment (for example L5 radiculopathy with foot drop due to lumbar disc herniation). In other cases, patients present at the emergency department without referral because of the paralysis of the foot and associated gait difficulties. A small group of patients presents in private clinics of neurologists and physical medicine and rehabilitation physicians. With the exception of some unique cases, almost all patients present in the acute setting. The first medical examination is almost never conducted more than three months after onset of symptoms. The statements above are based on experience and conducted patient interviews.

In every peroneal nerve entrapment case, diagnosis is made at the electrophysiology department. Involving the local electrophysiologist is therefore key to trial success. Ideally, the local electrophysiologist should be appointed as the non-surgical adjunct principal investigator.

## 7 ELIGIBILITY CRITERIA

### 7.1 Inclusion criteria

For inclusion in the study, the subject must fulfil the following inclusion criteria:

- Written informed consent to participate in the study must be obtained from the subject or proxy / legal representative prior to initiation of any study-mandated procedure
- EDX-documented peroneal nerve entrapment with persisting ( $10 \pm 4$  weeks) foot drop (MRC-score  $\leq 3$ )
- Imaging (ultrasound/MRI) performed to exclude a compressive mass
- Age  $\geq 18$  years

### 7.2 Exclusion criteria

- Subjects with posttraumatic or iatrogenic peroneal nerve injury
- Subjects with peroneal neuropathy due to a compressive mass (e.g. cyst, tumour)
- Peroneal nerve entrapment at other sites than the fibular head
- Bilateral peroneal nerve entrapment
- Patients with mental or physical problems that incapacitate them to participate in a physiotherapy program
- Psychiatric illness
- Pregnancy
- Planned (e)migration within 1 year after randomization to another country
- Subjects with previous foot drop
- Permanently bedridden subjects
- Subjects with neurological or musculoskeletal history which could impact foot drop assessment and/or gait analysis (e.g. polyneuropathy, hereditary neuropathy with pressure palsies, critical illness polyneuropathy, previous stroke, ankle surgery, ankle sprain, ...).

## 8 TRIAL PROCEDURES

### 8.1 Recruitment

All patients with foot drop due to peroneal nerve entrapment will be screened for eligibility at the screening visit. If a patient does not meet the inclusion criteria, or if a patient declines to participate, this will be documented in the screening log (ineligibility). Reasons for refusal to participate will also be documented in the screening log. Data will be anonymised. If a patient does not receive the allocated treatment after randomisation, the reason will be documented in the screening log and the reason will be communicated to the trial co-ordinator. In summary, the following information will be collected in the screening log:

- Screening number (not allowed to use initials, patient identification codes, not allowed to use any combination of elements that might allow the patient to be identified (GDPR))
- Date of consent (if applicable)
- Version of consent (if applicable)
- Date screened
- Eligible for enrolment?
- Study specific number (only to be completed for enrolled subjects)
- Date of randomization (if applicable)
- Ineligibility reasons (if applicable). If a patient enrolled in the study but cannot be randomized due to recovery, this will be clearly documented.

This allows for data collection in accordance with the 2010 CONSORT statement (Consolidated Standards of Reporting Trials) (65).

#### 8.1.1 *Patient identification*

Most patients, if not all, present within 3 months, due to the acute onset of paralysis. A significant percentage of patients with foot drop is referred (by the general practitioner) to the emergency department and will be detected in a very early stage. The reason for early referral is caused by the functional deficit resulting in difficulties walking and also due to the fact that the differential diagnosis of foot drop is broad, and certain diagnoses require urgent treatment. Other patients will seek medical attention without referral because of sudden gait problems. All but one interviewed patients sought medical attention within six weeks after the onset of symptoms, 63% presented in the first week.

The patient will be seen by a neurosurgeon, an orthopaedic surgeon, a neurologist or a physical medicine doctor. These departments will thus be heavily involved in this trial. In every peroneal nerve entrapment case, diagnosis is made at the electrophysiology department. Involving the local electrophysiologist is therefore key to trial success. Ideally, the local electrophysiologist should be appointed as the non-surgical adjunct principal investigator.

The treating physician will recruit the patient. At this stage, only the existing clinical care team has access to the patient records and therefore the treating physician will evaluate if the subject is a suitable candidate for the study based on the inclusion and exclusion criteria. There will be no recruitment through publicity (posters, leaflets, adverts or websites). Patient or disease registers will not be used to identify potential participants.

A small percentage of patients with foot drop due to peroneal nerve entrapment will present to neurologists and rehabilitation physicians in private practice, who do not always refer these patients to hospitals or surgical departments because they prefer a prolonged conservative treatment. An informative letter about the foot drop trial will be made to sensitize this group of treating physicians to refer their patients to a participating centre. These letters will be distributed through the representative national societies of both

specialisations. Furthermore, a manuscript reviewing the literature on peroneal nerve entrapment and discussing the foot drop study design was published in TNN (Tijdschrift voor Neurologie en Neurochirurgie).

### 8.1.2 Screening

Peroneal nerve entrapment will be confirmed by EDX after clinical investigation which is standard of care. The electrodiagnostic protocol will include motor nerve conduction studies [nerve conduction velocities, distal motor latencies, amplitudes of compound motor action potentials (CMAPs)], sensory nerve conduction studies and electromyography (EMG) evaluation during rest and voluntary contraction. EDX can identify other neuropathies/polyneuropathies or entrapment at other sites than the fibular head

Imaging (MRI or/and ultrasound) will be performed to document a compressive mass at the level of the fibular head (cysts/tumours). Through patient history and clinical investigation, the treating physician can identify posttraumatic or iatrogenic nerve injury, as well as subjects under the age of 18 years, previous foot drops and permanently bedridden patients. Eligibility screening procedures involve no investigations that emit ionising radiation. A knee X-ray is optional and warranted in traumatic peroneal nerve injury, but these patients are excluded. In a traumatic peroneal neuropathy, an x-ray of the knee is considered standard of care.

After the diagnosis of an EDX confirmed peroneal nerve entrapment at the level of the fibular head is made, the patient can be considered for inclusion in the trial, provided that ICF is obtained, and all other in- and exclusion criteria are fulfilled.

After the ICF has been signed, the local investigator or delegate contacts the clinical coordinator to allocate a subject number to the subject.

There are no intended payments to participants except reimbursement of reasonable travel expenses for any visits additional to normal care and reimbursement of expenses of extra investigations. There will be no extra payments to avoid a financial incentive to participate in the trial. Details on the amount of payment will be included in the informed consent form.

